3.4 Statistical Plan

3.4.1 Sample Size Determination

While the impact of asthma exacerbations on vascular function is currently unknown, we based our sample size calculation on our preliminary VTI data from 11 confirmed asthmatics who underwent a mannitol airway challenge to induce airway inflammation and bronchoconstriction. Based on these data, a total of 36 asthmatics and 36 controls in each group (stable asthma, healthy) would be sufficient to detect a 13% difference between these groups in VTI. Our preliminary data show a large increase in CRP in asthmatics experiencing an exacerbation vs. stable patients (7.3 vs. 0.5 mg/L, $p<0.05$), which would correspond to a substantial increase in CV risk³⁵, and be detectable with this sample size. An additional 8 participants per group will be recruited (i.e. 44 asthmatics, 44 stable asthmatics, and 44 controls) to compensate for potential dropouts. Sub-analyses evaluating potential sex-based differences will be exploratory and results will be considered hypothesis-generating.

3.4.2 Statistical Methods

The mean differences in FMD, systemic inflammation, and arterial stiffness for ED visit compared to the control group will be evaluated using an unpaired t-test. A within-factors repeated measures analysis of variance (ANOVA) will evaluate the mean differences between each assessment day for the exacerbation group to assess change in endothelial function during exacerbation as well as the recovery period. A similar evaluation will be used for arterial stiffness and systemic inflammation/immune response. A one-way analysis of covariance (ANCOVA) will be used to correct for shear rate in FMD for all groups, with both values being reported. An α -level of 0.05 will be used as the significance level for all statistical analysis, and all results will be reported as mean \pm standard deviation unless indicated otherwise.

4 Data Handling and Record Keeping

Data to be collected:

Outcome variables:

Endothelial function

Source of the data: Flow-mediated dilation test (see *measurement, endothelial function* above).

Time point for collection: Collected as the last assessment during the ED visit. For the 2 follow up visits, FMD will be done after arterial stiffness and prior to blood draw.

Who will collect the data: All data will be collected by trained research staff associated with the study.

Why the data is being collected: To evaluate the influence of acute asthma exacerbation on vascular health.

Is the data from a standardized tool: Yes.

What form will the data will take (e.g. binary, continuous (numeric), time to event): Continuous.

Arterial stiffness

Source of the data: pulse wave velocity test (see *measurements, arterial stiffness* above).

Time point for collection: At the ED, arterial stiffness will be collected after blood draw and prior to endothelial function. At the follow up visits, it will be collects as the primary assessment.

Who will collect the data: All data will be collected by trained research staff associated with the study.

Why the data is being collected: To evaluate the influence of acute asthma exacerbation on vascular health.

Is the data from a standardized tool: Yes.

What form will the data will take (e.g. binary, continuous (numeric), time to event): Continuous.

Systemic inflammation and immune response

Source of the data: Venous blood samples (see *measurements, systemic inflammation and immune response* above).

Time point for collection: At ED, blood will be collected as the primary assessment. At follow up visits, it will be collected as the final assessment.

Who will collect the data: All data will be collected by trained research staff associated with the study.

Why the data is being collected: To evaluate changes in systemic inflammatory levels and immune response throughout the study.

Is the data from a standardized tool: Yes.

What form will the data will take (e.g. binary, continuous (numeric), time to event): Continuous.

Explanatory variables and potential confounding variables:

Participant demographics, health history, and current status

Source of the data: interview with the participant as well as medical chart and ED physician. (see appendix 5)

Time point for collection: in the ED once hemodynamically stable and while receiving treatment. At follow up visits, additional information will be collected prior to assessments.

Who will collect the data: All data will be collected by trained research staff associated with the study.

Why the data is being collected: To ensure subject meet the inclusion/exclusion requirements, to obtain information on potential confounding variables, and to obtain general sample characteristics.

Is the data from a standardized tool: No, demographics will be collected according to the data collection document provided.

What form will the data will take (e.g. binary, continuous (numeric), time to event): Nominal, continuous or ordinal.

Perceived level of control and quality of life

Source of the data: The asthma control questionnaire (see appendix 1), asthma quality of life questionnaire (see appendix 2), and EQ-5D (see appendix 3).

Time point for collection: at 14 day post-discharge follow up.

Who will collect the data: All data will be collected by trained research staff associated with the study.

Why the data is being collected: To evaluate the current levels of perceived asthma control, disease specific quality of life and generalized quality of life.

Is the data from a standardized tool: Yes.

What form will the data will take (e.g. binary, continuous (numeric), time to event): Continuous.

Lung function

Source of the data: Pulmonary function test (see *measurements, pulmonary function* above)

Time point for collection: during a pre-test session, and at each baseline time-point.

Who will collect the data: All data will be collected by trained research staff associated with the study.

Why the data is being collected: To evaluate baseline lung function at each study day.

Is the data from a standardized tool: Yes.

What form will the data will take (e.g. binary, continuous (numeric), time to event): Continuous.

Physical Activity

Source of the data: Fitbit activity monitor

Time point for collection: monitor given at end of 48 hour follow up and retrieved from participant at 14 day follow up.

Who will collect the data: All data will be collected by trained research staff associated with the study.

Why the data is being collected: To evaluate average physical activity levels.

Is the data from a standardized tool: Yes.

What form will the data will take (e.g. binary, continuous (numeric), time to event): Ordinal.

Data collection forms and questionnaires are included as appendices.

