Asthma is a chronic inflammatory disease characterized by pulmonary inflammation and bronchoconstriction, with the prevalence of asthma steadily rising worldwide¹. **Asthma and Cardiovascular Disease:** While asthma is generally considered to be a disease of the airways, there are important systemic consequences which have predisposed people with asthma to become more likely to die from cardiovascular (CV) disease compared to non-asthmatics². Additional CV risks have been reported in people with severe asthma³, and there is a relationship between reductions in lung function and cardiac death⁴. To date, little is known in regards to the interaction between asthma exacerbations and CV risk. **Asthma and vascular dysfunction:** Brachial flow-mediated dilation (FMD) is used as a non-invasive tool to evaluate endothelial function⁵. Brachial FMD is impaired in people with coronary dysfunction⁶, and can predict future CV events better than traditional CV risk factors⁷. People with asthma have previously been shown to have impaired endothelial function compared to non-asthmatics⁸, but the underlying mechanism(s) are unclear. **Asthma, systemic inflammation, and CV risk:** Chronic systemic inflammation is an established risk factor and predictor of future CV events⁹, and levels of systemic inflammation are increased in asthma^{10,11}. Furthermore, while people with high levels of inflammation are more likely to suffer both first time and recurrent cardiac events^{12,13}, levels of systemic inflammation in asthma are related to disease severity and are the highest during asthma exacerbations^{10,11}. Previous studies have shown that systemic inflammation directly impairs vascular function¹⁴, and rodent work has shown that pulmonary inflammation can impair vascular function¹⁵. To-date, no study has examined how an asthma attack may affect vascular function and CV risk. Thus, to gain better understanding of the increased CV risks associated with asthma exacerbations, *the aim of this study is to evaluate vascular function and systemic inflammation during a naturally occurring asthma exacerbation.*

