3.1 Study Design

3.1.1 General Design

This study is a cohort study utilizing a repeated measure design. Asthmatic patients will be tested at 3 different time points:

- At the emergency department
- 48 hours following discharge
- 14 days following discharge

Stable asthmatic and non-asthmatic controls will be tested at two time points:

- Day 1
- 48 hours following Day 1

Vascular parameters such as flow mediated dilation (FMD; endothelial function) and pulse wave velocity (PWV; arterial stiffness) will be evaluated at each time point to assess vascular function. Blood samples will be obtained for analysis of systemic inflammatory response and immune response at each time point.

Participants will also be given Fitbit activity monitors for 7 days of monitoring, perform a full pulmonary function test (PFT) and complete 3 questionnaires; Asthma Control Questionnaire (ACQ), Asthma Quality of Life Questionnaire (AQLQ), and EQ-5D.

(A) Cohort studies

Definition of study groups:

Individuals experiencing an asthma exacerbation will be identified at the University of Alberta Emergency Department (ED). They will be recruited based on asthma being the primary physician diagnosis in the ED, with asthma being confirmed at a follow up visit using spirometry.

Stable asthmatic controls will be recruited from the general populations, as well as two local pulmonary clinics: The Lung Health Clinic, Edmonton, AB; and the University Lung Clinic, Edmonton, AB. These participants will be recruited if they have indicated they have been diagnosed with asthma. Both confirmed and unconfirmed asthmatics will be eligible.

Healthy controls will be recruited from the general population. They will be age-, sex, and BMI matched to the exacerbation group.

Blinding and avoiding bias:

Due to the nature of the study, blinding will not be applicable.

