3.2 Subject Selection and Withdrawal

3.2.1 Inclusion Criteria

To be eligible for this study, the participants have to be between the ages of 18 and 55. Asthmatics will have to present at the ED with an apparent asthma exacerbation. Stable asthma controls may have confirmed or unconfirmed asthma. Healthy control participants must be free of asthma.

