3.3 Study Procedures

Asthmatic patients will be tested at three different times:

- Day 1) ED visit
- Day 2) 48 hours post discharge
- Day 3) 14 days' post discharge

Day 1, participants will be recruited by the Emergency Medicine Research Group (EMeRG). They will receive standard emergency care for their asthma and once stabilized, informed consent will be obtained. A venous blood draw will be done prior to discharge. Once stabilized, the participant will be taken to a private area either within the ED department or [name]

lab in Clinical Sciences Building to ensure no interference with ED procedures. Applanation tonometry will be done to measure PWV, followed by FMD to determine endothelial function. **Day 2** the participant will return and the same assessments as Day 1 will be performed with the addition of spirometry according to standardized guidelines.¹⁸ Medication will not be withheld prior to this assessment. A Fitbit will be given along with instructions to wear the device for 7 days.

Day 3 will consist of the same measurements done in the ED for Day 1, with the addition of 2 quality of life questionnaires, the standardized Asthma Quality of Life Questionnaire (AQLQs) and the EQ-5D (5L), and the Asthma Control Questionnaire (ACQ), finishing with a full pulmonary function test including post-bronchodilator spirometry to evaluate for airway reversibility (i.e. asthma)¹⁹.

The participants are being tested 48 hours following the exacerbation to determine if systemic inflammation is further increased following an exacerbation, or if the exacerbation is when inflammation is at its peak. This will inform us on whether the exacerbation itself is the stimulus for increased systemic inflammation, or if it is a consequence of a stimulus in the days prior. The 14 day follow up was chosen based on the information that CRP is generally recovered to normal values after 14 days following stimulus,²⁰ as well, it is expected that lung function will have recovered 14 days following an exacerbation, as seen in other pulmonary disease exacerbations.²¹ Day 3 will tell us what average values for the participant would most likely be and allow us to compare the values obtained from the exacerbation against a personal reference value.

Stable asthmatics and healthy control participants will be tested at two different times:

- Day 1) date that participant is available for testing
- Day 2) 48 hours after Day 1

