Controls are being tested at two times to determine the degree of natural fluctuations in endothelial function, arterial stiffness, and systemic inflammation in healthy adults.

Measurements

Waist Circumference – Using a fabric tape measure, waist circumference will be measured at the level of the last rib to the nearest 0.1 cm after a normal expiration.¹⁷ This will be used as a measure of adiposity and will potentially be used as a covariate during statistical analysis.

Arterial stiffness - Arterial stiffness will be evaluated using pulse wave velocity (PWV) between the carotid and femoral arteries. After 10 minutes of resting in a dark, quiet room in the supine position, cPWV and pPWV will be recorded using applanation tonometry (Complior, Alam Medical, Saint Quentin Fallavier, France). A series of 10 consecutive beats will be taken with a minimum quality of 85%. The distance between the carotid and femoral artery, as well as the carotid and radial artery will be recorded in mm. PWV will be measured prior to FMD and blood collection, and will be taken on all 3 days of assessments. PWV is expressed as m/s and is calculated as $PWV = L/\Delta t$, with L being the distance between the two points and Δt being the time it takes for the pulse to get from site 1 to site 2.²²

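### The ED-visit t-test in section 3.4.2 names neither which of two control groups nor which control visit it uses, and the closer comparator, stable asthma, is neither matched nor adjusted for

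*Combined protocol and SAP*

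**What the plan says.** Section 3.1.1 defines two control groups, stable asthmatic and non-asthmatic, each tested on Day 1 and 48 hours later. Section 3.4.1 sizes each at 36, or 44 after allowing for dropout. Section 3.4.2 then refers to one control group: mean differences "for ED visit compared to the control group will be evaluated using an unpaired t-test". It does not say which group or visit is meant, or whether both groups are tested in turn.

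On comparability, the background states: "People with asthma have previously been shown to have impaired endothelial function compared to non-asthmatics". Section 3.1.1 says of the healthy controls: "They will be age-, sex, and BMI matched to the exacerbation group". Of the other group it says: "Stable asthmatic controls will be recruited from the general populations, as well as two local pulmonary clinics", and no matching is stated. Section 3.2.1 adds: "Stable asthma controls may have confirmed or unconfirmed asthma".

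Two adjustments are mentioned. Section 3.4.2 plans an ANCOVA for shear rate in FMD, reporting corrected and uncorrected values. Section 3.3 says that waist circumference "will potentially be used as a covariate during statistical analysis". Section 4 has potential confounders collected, but no model in 3.4.2 uses them.

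A within-person repeated-measures ANOVA is also planned for the exacerbation group. Day 14 is meant to let the investigators "compare the values obtained from the exacerbation against a personal reference value".

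**The concern.** Two analysts could follow section 3.4.2 to the letter and report different between-group results for the primary outcome, and the two results would mean different things. A difference from healthy controls may reflect having asthma rather than having an exacerbation. A difference from stable asthmatics is closer to the study question. However, that group is recruited from other sources without stated matching, so the difference could come from age, sex or BMI, or such an imbalance could hide a real effect. If the comparator is chosen after the data are seen, the reader cannot tell which of these has been reported.

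**Working it through.** **The plan's own figure.** The 36 per group cannot be reproduced, because section 3.4.1 gives neither SD nor power, and its 13% difference refers to VTI rather than FMD. Solved backwards (two-sided 0.05, t-based), 36 per group detects 0.67 SD at 80% power, which for a 13% difference implies a coefficient of variation of 13/0.67 = 19.4%. That is plausible but cannot be verified. The dropout step agrees: 36/(1 − 8/44) = 44.

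**Inputs.** n = 36 per group (3.4.1) and alpha 0.05 (3.4.2), taken as two-sided. All shifts and biases below are assumed, in SD units.

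**Formula.** For a standardised difference d, the unpaired t statistic is noncentral t with 2 × 36 − 2 = 70 degrees of freedom and noncentrality d × √(36/2) = 4.243d. The critical value is 1.994.

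**(a) ED versus healthy, no exacerbation effect, asthma alone shifts the outcome**

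| Assumed asthma shift (SD) | Noncentrality | Significant |
|---|---|---|
| 0.3 | 1.27 | 24% |
| 0.5 | 2.12 | 55% |
| 0.67 | 2.84 | 80% |
| 0.8 | 3.39 | 92% |

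These would be real group differences. The error would lie in attributing them to the exacerbation.

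**(b) ED versus stable asthma, unadjusted, no exacerbation effect.** Bias = covariate–outcome correlation × imbalance in the covariate.

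| Correlation × imbalance (SD) | Bias (SD) | Noncentrality | Type I error |
|---|---|---|---|
| 0.2 × 0.25 | 0.05 | 0.21 | 5.5% |
| 0.3 × 0.5 | 0.15 | 0.64 | 9.6% |
| 0.5 × 0.5 | 0.25 | 1.06 | 18.2% |

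If the imbalance works against a true 0.67 SD effect, the observed difference is 0.62, 0.52 or 0.42 SD, and power falls from 80% to 74%, 59% or 42%.

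**(c) What adjustment achieves.** Simulation of a three-group linear model with three covariates (20,000 runs; multiple R of 0.2, 0.3 and 0.5 paired with the three biases) gives type I error of 5.1%, 5.0% and 5.0% if the covariates carry all the bias. If they carry half, it is 5.1%, 6.3% and 9.6%. Adjustment therefore helps only with what is measured.

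**(d) What adjustment does not reach.** If treatment or test conditions at the ED visit add 0.1 to 0.3 SD (assumed), the noncentrality is 0.42 to 1.27 and ED versus stable asthma is significant in 7% to 24% of studies with no exacerbation effect. Adjusting for age, sex and BMI does not change this.

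**The case against.** Much of the case on the other side stands.

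- **Isolating the exacerbation.** A reader might infer that ED versus stable asthma isolates the exacerbation, or that it is independent evidence beside ED versus day 14. The documents do not support either. Both contrasts use the same ED measurement, taken after emergency treatment. Section 4 has blood drawn first in the ED but last at follow-up, and the fasting rule in section 3.3 covers only follow-up tests, when possible. The background also links inflammation and cardiovascular risk to asthma severity, which may differ between ED patients and stable asthmatics.
- **Pooled controls.** The singular wording might suggest that the two control groups are combined. Section 3.4.1 sizes each separately, so that reading is weak and nothing here relies on it.
- **No adjustment at all.** A reader might take the whole plan to be unadjusted. It is not: shear correction of FMD across all groups, with both values reported, is already planned. That ANCOVA standardises the FMD stimulus. It does not control for age, sex or BMI, and it does not cover arterial stiffness or inflammation.
- **The within-person analysis already answers the question.** It does avoid confounding by stable between-person differences, which is a real strength. It remains open to time effects, and the plan still includes a between-group test that has to be defined.
- **Assumed sizes.** Every shift and bias above is assumed. A range of 24% to 92% shows that the choice of comparator matters, but it is not an estimate for this study.

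**Conclusion.** The point holds as a gap in specification and in confounder control. The control group and visit are unnamed, and the more relevant comparator has neither stated matching nor a planned adjustment. No figure in the plan is shown to be wrong. Under the assumed inputs, the unadjusted ED versus stable asthma test has a type I error between 5.5% and 18%, and a significant ED versus healthy result can be common with no exacerbation effect. If the matching sentence was meant for both control groups, the text should say so; the unnamed group and visit would remain.

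It would go too far to say that naming stable asthma makes the exacerbation effect identifiable. ED versus stable asthma is the closer between-group contrast, with residual confounding that includes severity. ED versus day 14 is free of that but open to time effects. Both share the treatment, test-order and fasting effects of the ED visit.

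**What to change.** For each outcome (FMD, PWV, inflammation), replace the t-test with one linear model over the three groups on Day 1, giving two separate, unpooled contrasts:

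1. ED versus stable asthma, named as the main contrast.
2. ED versus healthy, tested second in fixed order.

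Adjust for pre-specified age, sex and BMI, and keep the planned shear covariate for shear-corrected FMD. Add two sensitivity analyses of the first contrast: one that also adjusts for a recorded severity marker where available (for example maintenance treatment or prior exacerbations), and one restricted to confirmed asthma in both the ED and stable arms, with confirmation defined in advance. Report the contrast beside ED versus day 14, state the weaknesses they share and those they do not, and describe neither as isolating the exacerbation.

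**Cost.** SAP wording and a few lines of code. The same demographics must be recorded in both control groups: the form in Appendix 5 is laid out for ED patients, and section 4 times first collection in the ED. If the covariates are uninformative, simulated power at 0.67 SD (50,000 runs) falls from 80.3% to 79.3%, or from 80.1% to 77.1% if each of the three is also imbalanced by 0.29 SD. Fixed order leaves alpha for the first contrast at 0.05, but ED versus healthy is not confirmatory if the first fails. Restricting to confirmed asthma reduces n in that sensitivity analysis, and unmeasured confounding remains.

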3.1.2 Primary Outcome Variable

Flow-mediated dilation (FMD) of the brachial artery following 5 minutes of forearm occlusion will be measured using our ultrasound machine (8L-RS 4.0-13.0 MHz probe, Vivid q, GE Healthcare, Mississauga, ON) and FMD data will be analyzed using FDA approved software available from Medical Imaging Applications (Coralville, IA, USA). FMD will be calculated as: (peak hyperemic diameter-baseline diameter)/baseline diameter x 100. Peak hyperemic brachial arterial velocity (and subsequently shear stress) will be determined using Doppler ultrasound, and used for normalization of FMD.

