Endothelial function - The endothelial function of the brachial artery will be evaluated after 10 minutes of rest in the supine position using ultrasound imaging (8L-RS 4.0-13.0MHz probe, Vivid q, GE Healthcare, Mississauga, ON). Baseline diameter of the brachial artery will be established, whereby the blood flow of the forearm will be occluded distal to the measuring site for the duration of 5 minutes. Upon release of the occlusion, the blood velocity and the brachial diameter will be monitored for 3 minutes, and later analyzed (Medical Imaging Applications, LLC, Coralville, IA, USA; EchoPAC PC software, version 110.x.x, GE Healthcare, Horten, Norway). Microvascular function will be evaluated as the velocity time integral-envelope of the first heartbeat of reactive hyperemia (VTI; m/s) and the velocity during reactive hyperemia (VRH) calculated as $VTI \times 60/HR$.²³ Shear stress during reactive hyperemia (SSRH) will subsequently then be calculated as $SSRH = 8 \times \text{flow} / \text{diameter}$ and as cumulative SSRH until the time of peak FMD%.^{24,25} FMD corrected for SSRH will be considered the main outcome for endothelial function in this study, and VRH and SSRH as indicators of microvascular function. Follow up tests will be conducted after a 12 hour fasting period when possible. Where applicable, the subjects will be asked to withhold any long-acting asthma medication for a minimum on 48 hours prior to the test, and short-acting asthma medications for 12 hours prior to the test.

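### Section 3.4.2 gives no valid shear-corrected analysis of the within-person course (ED, 48 hours, Day 14) of FMD, the declared main outcome

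*Combined protocol and SAP*

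**What the plan says.** Four statements bear on the point.

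- **Main outcome.** The endothelial function paragraph of section 3.3 states: "FMD corrected for SSRH will be considered the main outcome for endothelial function in this study". SSRH is shear stress during reactive hyperemia.
- **Time course.** Section 3.4.2 states: "A within-factors repeated measures analysis of variance (ANOVA) will evaluate the mean differences between each assessment day for the exacerbation group". The stated purpose is "to assess change in endothelial function during exacerbation as well as the recovery period". No covariate is named.
- **Shear correction.** Section 3.4.2 then adds: "A one-way analysis of covariance (ANCOVA) will be used to correct for shear rate in FMD for all groups, with both values being reported". It does not state the factor, the visit or visits used, or any participant term.
- **Second mention of shear.** Section 3.1.2 states: "Peak hyperemic brachial arterial velocity (and subsequently shear stress) will be determined using Doppler ultrasound, and used for normalization of FMD". It does not say whether this means a ratio, a covariate or something else.

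On the design, section 3.1.1 states "Asthmatic patients will be tested at 3 different time points" for the exacerbation group and "Stable asthmatic and non-asthmatic controls will be tested at two time points" for the others. Shear is obtained from each FMD test, so it takes a new value at every visit. No section names a repeated measures ANCOVA or a mixed model.

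**The concern.** Section 3.3 uses Day 14 as each patient's own reference for the exacerbation values, so the paired ED-to-follow-up change is central to the study. The method that respects the pairing names no shear covariate, and the method that corrects for shear does not respect pairing. Neither, as written, gives a shear-corrected within-person change.

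This matters if the hyperemic stimulus differs between visits. Measurement conditions do differ: the ED test follows emergency treatment, whereas follow-up tests are to be fasting where possible. The documents do not say whether shear will change as a result. If it does, raw FMD will move with it, and the repeated measures ANOVA cannot separate that movement from a change in endothelial function.

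**Working it through.** **1. The plan's own figure.** Section 3.4.1 gives 36 per group for a 13% difference in the velocity time integral (VTI), plus 8 for dropout (36 + 8 = 44). It gives no SD and no power, so 36 can be neither confirmed nor refuted. Solved backwards, two-sided at 0.05, the standardized difference is (1.960 + 0.842) × √(2/36) = 0.66 at 80% power, or 0.76 at 90%. This is a between-group figure for VTI. It is used below only for scale and as the source of n = 36.

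**2. Inputs for the illustration.**
- From the documents: n = 36 and 3 visits. Section 3.4.2 also gives alpha: "level of 0.05 will be used as the significance level for all statistical analysis".
- Assumed: FMD net of shear has SD 1 and within-person correlation (ICC) 0.5. Shear has SD 1 and ICC 0.5. The FMD-on-shear slope is 0.4 SD per SD. There is no true change in corrected FMD. ED shear is shifted by 0.5 or 1.0 SD.

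**3. Uncorrected repeated measures ANOVA.**
- Within-person variance: (1 − 0.5) + 0.4² × (1 − 0.5) = 0.58.
- Spurious ED shift in FMD: 0.4 × 0.5 = 0.2, or 0.4 × 1.0 = 0.4.
- Noncentrality: λ = n × shift² × (2/3) / variance. This gives 36 × 0.04 × (2/3) / 0.58 = 1.66, or 36 × 0.16 × (2/3) / 0.58 = 6.62.
- The critical value of F(2, 70) is 3.13. The noncentral F probability of exceeding it is **19%** or **61%**.

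Simulations of the same set-up gave 17 to 20% and 60 to 62%. The result depends on the ICC of FMD:

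| ICC | Variance | λ (0.5 / 1.0 SD) | False rejection |
|---|---|---|---|
| 0.3 | 0.78 | 1.23 / 4.92 | 15% / 48% |
| 0.5 | 0.58 | 1.66 / 6.62 | 19% / 61% |
| 0.7 | 0.38 | 2.53 / 10.1 | 27% / 80% |

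**4. Visit-level shear plus a participant term.** By simulation at ICC 0.5, false rejection is about 5% at both shifts. With no shear shift and a true ED effect of −0.4 SD, power is 0.67, against 0.60 for the uncorrected ANOVA.

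**5. Corrected FMD entered into the repeated measures ANOVA.** This keeps the pairing, but the result depends on how the correction is made (simulated, ICC 0.5, shifts of 0.5 / 1.0 SD):
- one slope from all visits, with no visit term: about 5% / 5.5%;
- one common slope, adjusted to the overall mean shear: 6.5% / 11%;
- a separate adjustment at each visit, centred on that visit's mean shear: 24% / 67%, because the between-visit shift is left in place.

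A ratio normalization was not examined.

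**The case against.** The best reply is that the plan can be read in a valid way. Section 3.3 defines the main endothelial outcome as corrected FMD, and section 3.4.2 says the repeated measures ANOVA assesses endothelial function. Together with the normalization in section 3.1.2, this lets corrected FMD at each visit enter that ANOVA. This stands, and it rules out saying that the ANCOVA is the only shear correction planned. It does not settle the matter: no method is given, and step 5 shows false rejection anywhere from about 5% to 67%, depending on a choice the plan leaves open.

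A reader might also infer that the plan treats repeat visits as independent. The documents do not support that.
- Pooling all 3 + 2 + 2 visits in a group ANCOVA would give type I error of about 11%, 16% and 20% at ICC 0.3, 0.5 and 0.7.
- Using visit as the one-way factor would cut power from 0.67 to 0.30 at ICC 0.5 for an ED effect of −0.4 SD.

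These figures describe possible misreadings. The correction for all groups most naturally means a between-group comparison, and at one visit that has one record per person and needs no participant term.

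Finally, corrected and uncorrected values are both to be reported, and section 3.3 keeps velocity and shear stress as separate microvascular indicators. A shear shift would therefore be visible, which reduces the harm. But the promise of both values is attached to the ANCOVA, and seeing a shift does not remove it from the paired test.

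**Conclusion.** The concern holds in this form: the plan declares a shear-corrected main outcome but specifies no valid shear-corrected analysis of its within-person course. On the most natural reading, the paired change is tested on raw FMD. A valid reading is open but not specified.

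The size is illustrative: about 19% or 61% false rejection for an ED shear shift of 0.5 or 1.0 SD, against about 5% with visit-level shear and a participant term. The slope, ICCs and shifts are assumptions; only the direction is robust. The 0.66 to 0.76 SD implied by the sample size falls inside the range of shifts used, but it is a between-group difference in VTI based on mannitol-challenge data. It is not evidence that patients' shear will change between ED and Day 14.

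Blinding is declared not applicable, so choosing among these analyses after the data are seen would leave real freedom over the main result. The model should be fixed beforehand.

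**What to change.** In section 3.4.2, make the primary analysis of FMD one linear mixed model with:
- a fixed effect for each group-by-visit cell (3 + 2 + 2 = 7 cells);
- that visit's shear as a time-varying covariate;
- a random participant intercept.

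Take ED minus 48 hours, ED minus Day 14, and ED minus each control group from this model, naming the control visit used. Fit it with and without shear, so that both values are still reported. State which fit is primary; section 3.3 points to the corrected one. State that the model takes precedence over the unpaired t-test and the repeated measures ANOVA for FMD, so that the same contrast is not tested twice without an order.

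Name one shear measure throughout: section 3.4.2 corrects for shear rate, while sections 3.1.2 and 3.3 refer to shear stress. Say what the normalization in section 3.1.2 means, or remove it. Splitting shear into the participant's mean and the visit's deviation from it is optional.

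The cost is revised wording and one model in standard software, with no new data. The downside is slightly more complex reporting.
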